# 5.4. Study Drug Administration: C-acetate

The C-acetate dose will be drawn and measured by the dose calibrator in the imaging facility and administered by IV injection to the patient under the direct supervision of a Nuclear Medicine Authorized User. The prescribed dose of C-acetate will be approximately 20 mCi, with an expected range of the injected dose for most

studies of 15 - 25 mCi at the time of injection, a lesser dose may be injected if, in the opinion of a Nuclear Medicine Authorized User complete imaging data could be generated. In the dose of C-acetate, only a small fraction of the acetate molecules are radioactive. C-acetate is administered to subjects by intravenous injection. The injection or imaging procedure will be terminated in any patient who exhibits anaphylaxis, significant dyspnea or chest pain. For additional study drug information refer to the Investigator's Brochure for C-acetate.

# 6. Study Procedures and Study Calendar

#### **STUDY CALENDAR**

	Screening Assessments 	Baseline Assessments	Day of  C-Acetate PET/CT scan
Informed Consent	Х		
Demographics	X		
Brain MRI 	X		
Amyloid PET/CT scan 	X		
MMSE 	X		
Lumbar Puncture 	X	Х	
Neuropsychological test battery 		X	
Pfeffer Functional Activities		X	
Questionnaire (FAQ)			
 C-acetate PET/CT scan			X
Venous blood sampling 			X
Adverse Event Evaluation 			X

<sup>1 Patients that have a Brain MRI scan previously performed within 6 months of study enrollment may not need to repeat this scan, images will be reviewed by a physician to determine if the MRI can be used for the purposes of the study, this may occur prior to consent and enrollment in this study.

- a. Trail Making Test A and B
- b. Category Fluency
- c. 30-item Boston Naming Test
- d. Rey Auditory Verbal Learning Test (AVLT) for episodic memory
- e. Digit-symbol for processing speed, executive functioning
- f. Lexical fluency (F words in 1 min).
- g. Pfeffer Functional Activities Questionnaire (FAQ)
- h. Geriatric Depression Scale (GDS)
- i. Optional: ADAS-cog, if time permits

<sup>2 Many patients will be recruited from other studies that perform Amyloid PET/CT scans (typically using F-florbetaben or F-florbetapir) the amyloid PET/CT scan should be performed within 6 months of study enrollment. If a subject has not undergone an Amyloid brain PET/CT as part of IDEAS or clinically then they will be asked to undergo a research Amyloid brain scan after they have consented for this study. If it is done as part of this research study the FDA approved radiotracer [F]Florbetaben (Neuraceq) will be used according to the standard Penn imaging procedure. Only Cohort 1 and Cohort 3 patients will be required to have an Amyloid PET/CT scan. Scan results will be reviewed prior to scheduling the C-Acetate PET/CT scan.

<sup>3 Mini Mental State Exam

<sup>4 Optional: Patients who have previously had CSF stored or tested will not be asked to repeat these procedures. Timing of this will vary depending on if the patient has already had this done as part of clinical care or another study. If it is being performed prior to the imaging, lumbar puncture should occur a minimum of 48 hours prior to the C-Acetate PET/CT scan.

<sup>5 Neuropsychological test battery will include the following tests:

 Venous blood samples will be taken during the C-Acetate PET/CT imaging session in order to measure radioactive counts in the blood. If a second IV line is not able to be successfully accessed or an investigator does not think the patient can tolerate a second IV for blood draws this may be omitted.

 Follow up may occur by telephone or in person, depending on the subject's schedule. Follow up should take place the next available business day (i.e. not a weekend or a holiday). The AE monitoring period is 10 hours following C-acetate injection

 Screening assessments may be performed over multiple days

# 6.1. Initial screening and baseline visits prior to C-acetate PET/CT scan

The investigator will provide for the protection of the subjects by following all applicable regulations. These regulations are available upon request from the sponsor. The sponsor and IRB must review the informed consent form used during the informed consent process, and it must be available for inspection.

Before any procedures specified in this protocol are performed, a subject must:

- Be informed of all pertinent aspects of the study and all elements of informed consent.
- Be given time to ask questions and time to consider the decision to participate.
- Voluntarily agree to participate in the study.
- Sign and date an IRB/IEC-approved informed consent form.

Potential subjects for Cohort 1 will be identified by treating physicians at Penn Memory Center or their referral clinics within the University of Pennsylvania Health System. Potential subjects will be approached by their treating physician about participation in the study. If the patient is interested in participation they will be contacted by one of the investigators and/or study staff for recruitment. The research team will review the study and obtain consent after subjects have adequate opportunity to discuss the study and have all questions answered.

Potential subjects for Cohort 2 and Cohort 3 may be recruited from the subject population of a current study investigating neuroinflammation in late life depression and health controls (IRB 819654) from the healthy control group and from the PMC research cohort. Subjects in that ongoing study all receive MRI and LP and would be evaluated for additional eligibility criteria for this imaging protocol and will be approached by study personnel about participation.

Screening may take place over several days. All screening assessments should be performed prior to the C-Acetate PET/CT imaging session.

Screening assessments include:

- 1. Demographics (age, gender, race, ethnicity)
- 2. Medical history (may be taken from medical record review)
- 3. Concomitant medications recorded
- 4. Mini Mental State Exam (MMSE)
- 5. Brain MRI including standard clinical sequences and volumetric MRI. Patients that have a Brain MRI scan that was performed within 6 months of study enrollment may not need to repeat this scan; images will be reviewed by a

- physician to determine if the MRI can be used for the purposes of the study, this may occur prior to consent and enrollment in this study.
- 6. Amyloid brain PET/CT scan (required for Cohort 1 and Cohort 3) In order to reduce costs, subjects may be recruited from other studies that perform amyloid PET/CT (typically using F-florbetaben or F-florbetapir. The CMS coverage with evidence development IDEAS amyloid PET/CT study starts recruitment February 2016, providing Medicare reimbursement for clinical amyloid PET/CT scans for the first time; Penn will be a site for this study and we anticipate that many patients being considered for this experimental C-Acetate imaging protocol will qualify to undergo clinical Amyloid PET/CT as part of the IDEAS registration trial (IRB 824052). Amyloid PET/CT scans should be completed within 6 months of study enrollment. If a subject has not undergone an Amyloid brain PET/CT as part of IDEAS or clinically then they will be asked to undergo a research Amyloid brain scan after they have consented for this study. If it is done as part of this research study the FDA approved radiotracer [18F]florbetaben (Neuraceq) will be used according to the standard Penn imaging procedure. For Cohort 1 and Cohort 3, the Amyloid brain PET/CT scan will be reviewed by an investigator or designee prior to scheduling the C-Acetate PET/CT scan, for subjects in Cohort 2 if an Amyloid PET is available it will be reviewed, however, it is not required for participation in Cohort 2.. If the Amyloid PET/CT scan is deemed to be negative then the subject will be considered non-evaluable and will be withdrawn from the study. Non-evaluable subjects will be replaced in the study enrollment total.

Baseline assessments: may be performed the same day as screening assessments or on a separate day within 90 days of the C-Acetate PET/CT, including the day of that study.

### Amyloid brain PET/CT scan (if performed as a research scan for this study)

The following procedures will be done on the day of the [18F]florbetaben PET/CT scan

- Weight and height will be recorded
- Injection of [F]florbetaben

The patient will be made comfortable in a preparatory room, one intravenous line (IV) will be placed, usually one in the arm or hand. Patients will receive approximately 8.1 mCi (± 20%) of [¹8F]florbetaben intravenously by trained nuclear medicine staff, a lesser dose may be injected if, in the opinion of a Nuclear Medicine Authorized User complete imaging data could be generated.

Patients will be escorted to the scanner room and positioned in the PET/CT scanner with arms by the side. According to standard procedures used for clinical amyloid PET/CT scans at the Hospital of the University of Pennsylvania, an approximately 15 minute static brain PET scan will be obtained starting at approximately 90 minutes post-injection. A low-dose brain CT scan will be acquired according to standard PET/CT imaging procedures; this CT is used for attenuation correction in PET scan processing. The CT can be performed either before or after the PET transmission scan. There are no separate diagnostic CT scans performed as part of this research.

# **Brain MRI**

If the subject has undergone a brain MRI within 6 months of study entry it may meet the study requirements for MRI imaging; the scan will be reviewed by a study physician to determine whether it can be used for the purposes of this study. If the subject does not have a Brain MRI that is deemed acceptable within 6 months of study enrollment they will be asked to undergo a research Brain MRI after they have consented for this study. Prior to the brain MRI they will be asked to complete an MRI safety form which is a standard assessment form, created by the Department of Radiology at the Hospital of the University of Pennsylvania to assess history of specific prosthesis, surgical implants, and other MRI contraindications. The greatest risk is a magnetic object flying through the air toward the magnet and hitting the subject. Some of the pulse sequences and/or RF coils are not FDA approved but are considered to pose no more than minimal risk. There is no known health risk associated with exposure to magnetic fields during an MRI. There are minimal risks from the loud noise associated with the MRI scanner and from discomfort of lying on a hard surface. Implanted medical devices and metallic foreign fragments inside the body may pose a risk is subjects were to enter the MRI magnet room.

Incidental Findings: It is possible that during the course of the research study, the research staff may notice an unexpected finding(s). Should this occur, the finding(s) will be considered by the appropriate personnel and the PI will determine if the patient should be informed of these findings. These possible finding(s) may or may not be significant and may lead to anxiety about a condition and to further work-up by the subject's physician.

# Neuropsychological testing

Neuropsychological test battery will include standardly used tests including:

- j. Trail Making Test A and B
- k. Category Fluency
- I. 30-item Boston Naming Test
- m. Rey Auditory Verbal Learning Test (AVLT) for episodic memory
- n. Digit-symbol for processing speed, executive functioning
- o. Lexical fluency (F words in 1 min).
- p. Pfeffer Functional Activities Questionnaire (FAQ)
- q. Geriatric Depression Scale (GDS)
- r. Optional: ADAS-cog, if time permits

### Optional: Cerebrospinal fluid (CSF) by Lumbar Puncture (LP).

Some subjects may be asked to undergo an optional lumbar puncture to collect CSF. If subjects agree to the LP it will be performed by a qualified physician who is experienced in performing the procedure. Subjects, or their designated decision maker, will call the investigator to report any adverse events associated with the LP procedure. Patients who have previously had CSF collected and stored or tested will not be asked to repeat these procedures. If it is being performed prior to the imaging, lumbar puncture should occur a minimum of 48 hours prior to the C-Acetate PET/CT scan.

The following additional patient data may be self-reported by the patient or obtained from medical chart review: demographics (including gender, date of birth and race).

# 6.2. Day of C-acetate PET/CT scan

Consent for administration of the investigational drugs will be discussed again with the patient on the day of the PET/CT scan and documented on a supplemental consent form by a delegated Nuclear Medicine Authorized User prior to administration of any study drugs.

The following procedures will be done on the day of the C-acetate PET/CT scan

- Weight and height will be recorded
- Injection of C-acetate.

The patient will be made comfortable in a preparatory room, two intravenous lines (IVs) will be placed, usually one in each arm or hand. The location of the IV used for injection will be documented. Patients will be escorted to the scanner room and positioned in the PET/CT scanner with arms by the side. Patients will receive approximately 20 mCi of C-acetate intravenously under the direct supervision of a Nuclear Medicine Authorized User (AU). The prescribed dose of C-acetate will be approximately 20 mCi, with an expected range of the injected dose for most studies of 15 to 25 mCi at the time of injection, a lesser dose may be injected if, in the opinion of a Nuclear Medicine Authorized User complete imaging data could be generated.

Subjects will undergo a 60 minute dynamic brain PET/CT scan starting at approximately the same time as the injection of C-Acetate. A low-dose brain CT scan will be acquired according to standard PET/CT imaging procedures; this CT is used for attenuation correction in PET scan processing. The CT can be performed either before or after the PET transmission scan. There are no separate diagnostic CT scans performed as part of this research.

Venous Blood Sampling: Subjects will have two intravenous (IV) lines placed prior to start of scanning, these will generally be placed one in each upper extremity, one IV will be used for injection of the tracer, the other IV will be used for collecting venous blood samples during the course of the scanning protocol. The side of the body used for injection will be documented.

Venous Blood Sampling: Venous blood samples will be collected at approximately 2, 5, 10, 20, 40 and 60 minutes post-injection to measure radioactive counts in the blood. The actual time of each blood draw will be recorded. Sampling may be reduced to fewer time points if experience from the first subjects indicates fewer time points will be sufficient for analysis. The total amount of blood drawn for venous sampling will be approximately 12 mL (about 3 teaspoons). If a second IV line is not able to be successfully accessed or an investigator does not think the patient can tolerate a second IV for blood draws this may be omitted at the discretion of an investigator, this will be recorded in the CRF and will not be considered a protocol deviation.

Adverse events that are grade 3 or higher will be recorded for the period up to 10 hours post injection of the radiotracer. Research personnel will conduct follow up by telephone

or in person, depending on the subject's schedule. Follow up should take place the next available business day (i.e. not a weekend or a holiday).

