### 9.2. Recording of Adverse Events

At each study visit session, the Principal Investigator or designee, must seek information from the subject in reference to any adverse events specific to imaging procedures or injection of C-acetate that may have occurred by specific questioning and as appropriate by examination. Information on all adverse events should be recorded in as much detail as possible on a source document or the medical record and entered on the Adverse Event Log.

All adverse events occurring during the AE reporting period of 10 hours post C-acetate injection will be recorded. The clinical course of each event should be followed until resolution, stabilization, or until it has been determined that the study treatment or participation is not the cause. Serious adverse events that are still ongoing at the end of the study period must be followed up to determine the final outcome. Any serious adverse event that occurs after the study period and is considered to be possibly related to the study imaging or study participation should be recorded and reported immediately.

The PI should be contacted immediately to determine the reporting requirements for the event as outlined in the protocol.

The clinical course of each event should be followed until resolution, stabilization or until it has been determined that the investigational agent or study procedure is not the cause of the event.

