# 9.3. Reporting of Adverse Events and Serious Adverse Events

It is the responsibility of the Principal Investigator to determine the grade, attribution and expectedness of the event and if the event is reportable according to the requirements outlined in the protocol.

For this investigational agent the following criteria should be met to consider an adverse event reportable:

- The event occurred within 10 hours after the injection of the investigational agent, 

  11C-acetate.
- All unexpected events regardless of grade or attribution.
- Expected events that are grade 3 or higher.
- Expected events that are possibly, probably or defiantly related to the investigational agent.

When reporting please supply a narrative with as much description of the event as possible (chart note is acceptable) along with the completed AE Log or CRF signed and dated by the Principal Investigator.

The narrative should include:

Protocol number and name
Subject number
Date of onset
A detailed description of the event
If the study procedure was discontinued

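### For the same 10 hours after 11C-acetate injection, section 6.2 records adverse events of grade 3 or higher, section 9.2 records all of them, and section 9.3 makes some grade 1-2 events reportable

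*Combined protocol and SAP*

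**What the plan says.** Three parts of the combined protocol and SAP deal with adverse events in the 10 hours after the tracer injection.

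- **Section 6.2 (day of the scan):** "Adverse events that are grade 3 or higher will be recorded for the period up to 10 hours post injection of the radiotracer". The sentences that follow direct the telephone or in-person follow-up on the next business day.
- **Section 9.2 (recording):** "All adverse events occurring during the AE reporting period of 10 hours post" acetate injection are to be recorded, with no grade limit. The same section says "Information on all adverse events should be recorded in as much detail as possible on a source document or the medical record" and adds entry on the Adverse Event Log.
- **Section 9.3 (reporting):** besides the 10-hour time condition, the list of reportable events includes "All unexpected events regardless of grade or attribution" and "Expected events that are possibly, probably or defiantly related to the investigational agent". Neither has a grade limit. Only one criterion does: expected events of grade 3 or higher.

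Section 9.3.1 requires reportable events to reach the sponsor within 24 hours, with the log and a narrative enclosed.

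On the start of the period, section 9.1 (Adverse Event Reporting Period) opens it when any study procedure begins and closes it 10 hours after acetate. Study calendar footnote 7 and sections 9.2, 9.3 and 9.3.2 count only from the injection.

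**The concern.** Sections 6.2 and 9.2 use the same verb, the same starting event and the same 10 hours, but different thresholds. A stated threshold of grade 3 has no function if everything is recorded, so a reader of 6.2 may reasonably take it as the rule for scan day. No text separates the two, for instance by assigning 6.2 to the case report form and 9.2 to source documents.

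The difference matters because reporting depends on recording. An event that nobody writes down cannot reliably be sent to the sponsor with a log entry and a narrative. Section 1.3 also says that the study's own monitoring will be used to follow the tracer's safety, and that monitoring is weaker if mild events are recorded by some staff and not by others.

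**Working it through.** The point needs no formula. The check sorts events within 10 hours of injection by grade (section 9.1 scale, 1 to 5), expectedness and attribution, and asks what each section does with them.

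| Event within 10 hours of injection | Named in the 6.2 sentence | Recorded under 9.2 | Reportable under 9.3 |
|---|---|---|---|
| Grade 3-5 | Yes | Yes | Yes |
| Grade 1-2, unexpected, any attribution | No | Yes | Yes |
| Grade 1-2, expected, at least possibly related to the agent | No | Yes | Yes |
| Grade 1-2, expected, unlikely related or unrelated | No | Yes | No |

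**Reading of 9.3.** The list is introduced by "For this investigational agent the following criteria should be met to consider an adverse event reportable". The four items cannot all be required at once, because no event is both expected and unexpected. The workable reading, used in the table, is the time condition plus any one of the other three.

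**Result.** In rows two to four, 6.2 and 9.2 differ. In rows two and three, the event left out of the 6.2 sentence is also one that must go to the sponsor.

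**Worked example.** Take mild itching or rash after injection, judged possibly related.

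1. Section 1.3 lists both as symptoms of an allergic reaction, so under the section 9.1 definition they are described in the protocol and count as expected. Section 1.3 also says that no adverse reactions to the injection are anticipated, so the label can be argued.
2. If the event is expected, it is reportable as at least possibly related. If it is unexpected, it is reportable at any grade. The result is the same either way.
3. Section 9.2 requires a record, and section 9.3.1 requires a sponsor report within 24 hours.
4. The 6.2 sentence does not cover the event, because it is below grade 3.

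**Exposure.** Each subject has one acetate injection. The planned cohorts are 14 + 6 + 5 = 25 evaluable subjects, so 25 ten-hour windows are affected. Section 1.3 reports no tracer-related events in about 3,450 people studied, so few are likely here.

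**Start of the period.** Section 9.1 begins with the first study procedure; footnote 7, 9.2, 9.3 and 9.3.2 begin at injection. The calendar marks adverse-event evaluation on the acetate day only. The two starting points differ for events after a research MRI, florbetaben scan or lumbar puncture done before the acetate scan.

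**The case against.** The strongest reply is that 6.2 does not say that only events of grade 3 or higher are recorded. Section 9.2 is the section dedicated to recording, it already has the wider rule, and it is where the log is set up. It also says that the investigator or designee "must seek information from the subject in reference to any adverse events specific to imaging procedures or injection of" acetate. Staff who follow 9.2 lose nothing. This stands, and it makes the harm conditional: events are missed only if someone works from the 6.2 sentence. It does not remove the contradiction, because 6.2 is the text for the day in question and nothing says that 9.2 prevails.

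On the start of the period, section 9.1 describes what is normal, and 9.3 is framed around the investigational agent. Other routes catch many events: the telephone report after lumbar puncture (6.1), related hospitalizations (9.1), questioning about imaging procedures at each visit (9.2), and unanticipated problems reported to the IRB (9.3.2). What is left is mainly non-serious events, so this part is minor.

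Some stronger readings are tempting but not supported:

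- **That the end of the period is also in conflict.** Every place that states an end gives 10 hours. The rule for "Any serious adverse event that occurs after the study period and is considered to be possibly related to the study imaging or study participation" reads as an exception, and the next-business-day contact is when staff ask, not a different window.
- **That events after a post-scan lumbar puncture are lost.** Footnote 4 does not exclude one, but the calendar and section 6.1 place the procedure at screening or baseline, before the scan.
- **That bruising or dizziness from the IV lines shows the same conflict.** The lines are placed before injection, so onset at placement falls outside the 10 hours.
- **That a planned safety estimate is distorted.** The protocol has no safety objective, safety analysis variable or event-rate analysis. An upper limit calculated from zero events would be numerically the same under either rule; only the grades it describes would differ.

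**Conclusion.** The contradiction is real and should be corrected. Sections 6.2 and 9.2 set different recording thresholds for the same 10 hours, and 9.3 with 9.3.1 makes some of the events omitted by 6.2 reportable to the sponsor. Confidence is high on this.

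The consequence is limited. It concerns grade 1-2 events in about 25 single-injection windows, arises only where staff apply 6.2 rather than 9.2, and probably involves few tracer events. It does not touch the comparison of acetate uptake between MCI subjects and controls. The conclusion assumes that the 9.3 list means the time condition plus any one other criterion.

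The differing start of the period is a true inconsistency of lesser weight, held with moderate confidence.

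**What to change.** Reconcile the 6.2 sentence with 9.2 and 9.3, either by deleting its grade threshold or by replacing it with a reference to 9.2. At the least, recording must cover every event that 9.3 makes reportable.

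As a minor edit, state one start for the period in 9.1, 9.2, 9.3, 9.3.2 and calendar footnote 7. If it is to run from injection only, say which existing route covers events after earlier research procedures, including those in a Cohort 1 subject withdrawn for a negative amyloid scan before receiving acetate.

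Two wording clarifications could be made at the same time, although the point does not depend on them. The lists in 9.3 and 9.3.2 could be written as the time condition plus any one other criterion, if that is the intent. Section 9.3.2 could say whether expected, low-grade, related events go to the IRB, since its opening is limited to unforeseen events that raise risk while its list is wider.

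The cost of the main change is a sentence or two and slightly more event logging, with no effect on the sample size or the primary comparison.
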